7.3 Exploratory analysis

Exploratory analyses will be performed to determine if any relationships exist between disease status at study entry, prior treatments (chemotherapy and other cancer treatments), tumour genetic markers or biomarkers and efficacy outcomes for patients.

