
Criteria for Evaluation
	
Safety: to be assessed through the analysis of routine laboratory tests (haematology, serum chemistry, urinalysis), physical examinations, vital signs, and ECOG status. Adverse event monitoring will be performed and assessed using the CTCAE National Cancer Institute Common Terminology Criteria for Adverse Events, Version 4.03 (CTCAE) scoring system.
 
Efficacy: All efficacy assessments will be performed at the discretion of the Investigator but at a minimum should include a baseline assessment (CT scan, ECOG assessment) and follow-up assessments at a minimum of every 12 weeks while receiving study drug. Tumor response and progression-free survival will be assessed using standard RECIST criteria.
 
Pharmacokinetics: blood and 24 hour-urine samples will be analysed to determine the primary idronoxil metabolites and the primary route of excretion.
 
Biomarkers: Ceramide and sphingosine-1-phosphate (related to the molecular target of idronoxil) and ENOX2 will be assessed at baseline and at completion of idronoxil therapy per cycle. Biomarker and plasma idronoxil levels to be correlated with anti-cancer activity and any toxicity.

Statistical Methods
	
Statistical analyses will be primarily descriptive in nature and statistical hypothesis testing will not be performed. All patients will be included in the evaluation of safety. Data will be presented by Cohort, by idronoxil and carboplatin dosages, and by tumour type.

Inclusion Criteria
	
 
1. Provision of informed consent.
 
2. Male or female <math>\geq 18</math> years of age.
 

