### 6.2 SECONDARY OBJECTIVES

- to characterise some key pharmacokinetic features of idronoxil when administered rectally
- to determine if various biomarkers of idronoxil biologic activity have any correlation to the efficacy or toxicity of idronoxil in combination with carboplatin.

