### **10.2.3 Pharmacokinetic and Biomarker**

Idronoxil levels will be assayed both in plasma samples and 24-hour urine samples collected from patients in both the Phase Ia and Phase Ib Arms of the Study. See section 10.4.6.

Biomarkers (ceramide, sphingosine kinase and ENOX 2 levels) will be measured in the same plasma samples collected for pharmacokinetic analysis. See section 10.4.7.

Plasma collection and 24-hour urine collection procedures are outlined in APPENDIX B.

Idronoxil and biomarker assays will be undertaken by the Sponsor performed by a designated laboratory.

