### 13.2 STATISTICAL METHODOLOGY

This section describes the planned statistical analyses in general terms. A complete description of the statistical analysis will be specified in a statistical Analysis Plan (SAP) finalised prior to completion of the study.

The primary objectives of this study are to determine

- (a) the tolerability, adverse event profile and any dose limiting toxicities (DLTs) of idronoxil (as NOX66) in combination with carboplatin in patients with refractory solid tumors, and
- (b) the ability of idronoxil (as NOX66) in combination with carboplatin to deliver a meaningful anti-cancer effect in refractory tumours considered unlikely to respond to carboplatin.

Secondary objectives are:

- 1) to characterize the pharmacokinetic profile of idronoxil administered rectally as NOX66, and
- 2) to determine any correlation between biomarkers of idronoxil biological activity and any clinical anti-tumor activity or toxicity observed in patients treated with NOX66.

These objectives are to be addressed in the context of an open-label, dose-escalation study; therefore, statistical hypothesis-testing will not be performed, and analyses will be primarily descriptive in nature.

All patients will be included in the safety evaluation. Data will be presented by dose cohort. Data from Study NOX66-001A will be used to guide dosing for future Phase II trials.

**Populations for Analysis:** There will be three study populations defined for this study.

The safety population will consist of all patients who received at least one dose of idronoxil. This population will be used in all safety summaries.

The efficacy population will consist of all patients with measurable or evaluable disease at baseline who complete at least 1 cycle of treatment and undergo at least one follow-up tumor

evaluation.

The pharmacokinetic/biomarker population will be a subset of the safety and efficacy populations and consist of all patients who have sufficient idronoxil plasma data for analysis. All such patients will be evaluated unless significant protocol deviations have impacted the data. Changes to the procedures, which may impact the quality of pharmacokinetic data, will be considered significant protocol deviations. Examples include sample processing errors that lead to inaccurate bio- analytical results and/or inaccurate dosing on the day of pharmacokinetic sampling.

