2.3 Study objectives

The primary objectives of this study are:

- to determine the tolerability, adverse event profile, maximum tolerated dose (MTD), and dose-limiting toxicities (DLTs) of NOX66 in a suppository dosage form in patients with refractory solid tumours, both as a single agent and in combination with carboplatin
- to determine if NOX66 in a suppository dosage form is able to combine with a standard dosage of carboplatin to produce a meaningful anti-cancer effect in solid tumours considered to be refractory to cytotoxic chemotherapy
- to determine if NOX66 in a suppository dosage form (NOX66) is able to combine with a dosage of carboplatin two-thirds of the standard dosage to produce a meaningful anti-cancer effect in solid tumours considered to be refractory to cytotoxic chemotherapy.

The secondary objectives are:

- to characterise some key pharmacokinetic features of NOX66 when administered rectally
- to determine if various biomarkers of NOX66 biologic activity have any correlation to the efficacy or toxicity of NOX66 in combination with carboplatin.

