3.1 Analysis populations

There will be three study populations defined for this study.

The safety population will consist of all patients who received at least one dose of NOX66. This population will be used in all safety summaries.

The efficacy population will consist of all patients with measurable or evaluable disease at baseline who complete at least 1 cycle of combination treatment and undergo at least one follow-up tumour evaluation.

The pharmacokinetic/biomarker population will be a subset of the safety and efficacy populations and consist of all patients who have sufficient NOX66 plasma data or biomarker plasma data for analysis. All such patients will be evaluated unless significant protocol deviations have impacted the data. Changes to the procedures, which may impact the quality of pharmacokinetic data, will be considered significant protocol deviations. Examples include sample processing errors that lead to inaccurate bio-analytical results and/or inaccurate dosing on the day of pharmacokinetic sampling.

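### The SAP has no analysis for the toxicity half of the biomarker objective, and it ties the PK/biomarker population to having a scan

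*SAP*

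**What the plan says.** SAP 2.3 sets the secondary objective: "to determine if various biomarkers of NOX66 biologic activity have any correlation to the efficacy or toxicity of NOX66 in combination with carboplatin". Protocol 6.2 matches it: biomarkers should "have any correlation to the efficacy or toxicity of idronoxil in combination with carboplatin". Protocol 13.2 restates it as "to determine any correlation between biomarkers of idronoxil biological activity and any clinical anti-tumor activity or toxicity observed", gives no method, and leaves the full analysis to the SAP. The synopsis (Biomarkers) also wants plasma idronoxil levels related to both anti-cancer activity and toxicity.

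SAP 7.3 then limits the relationship analysis to disease status at entry, prior treatments and "tumour genetic markers or biomarkers and efficacy outcomes for patients". It names no population, time point or summary measure.

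On populations, SAP 3.1 states: "The pharmacokinetic/biomarker population will be a subset of the safety and efficacy populations". The efficacy population there requires one completed cycle of combination treatment and a follow-up tumour assessment. Section 11 puts plasma concentrations and PK coefficients on a PK population, but the biomarker table and figure on the Safety population.

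On analytes, the synopsis lists "Ceramide and sphingosine-1-phosphate (related to the molecular target of idronoxil) and ENOX2", while Protocol 10.2.3 says "Biomarkers (ceramide, sphingosine kinase and ENOX 2 levels) will be measured".

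**The concern.** An objective that names two outcomes needs an analysis of both. Here only efficacy has one. Any biomarker-toxicity result would be devised after the data are seen, or would not appear at all.

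The population rule raises a second difficulty. Whether a patient has had a scan says nothing about whether their plasma data are usable. Patients who stop the combination before a scan, including those who stop for toxicity, are relevant to a toxicity question, yet the definition removes them from the PK outputs. Because 3.1 and section 11 disagree, a programmer also cannot tell which patients a biomarker relationship analysis under 7.3 should use.

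**Working it through.** The documents give no figure for this objective, so there is nothing to reproduce. Most of the check is a comparison of text.

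**1. Objective against analysis**

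| Place | Efficacy | Toxicity |
|---|---|---|
| SAP 2.3, Protocol 6.2 and 13.2 (objective) | named | named |
| Protocol synopsis, Biomarkers (adds plasma levels) | named | named |
| SAP 7.3 | biomarkers related to outcome | absent |
| SAP 8.2 | not applicable | adverse events tabulated, no biomarker or plasma level |
| SAP 8.6 | not applicable | biomarker change from baseline only |
| SAP 11 | no biomarker-by-response output listed | no biomarker-by-toxicity output listed |

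The toxicity cell is empty everywhere that an analysis could sit.

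**2. Population chain (SAP 3.1)**

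- Safety: at least one dose.
- Efficacy: disease at baseline, plus one completed combination cycle, plus one follow-up assessment.
- PK/biomarker: inside both of these, plus sufficient plasma or biomarker data.

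I take the PK population of section 11 to be this third set, since no other is defined. Protocol 13.2 carries the same subset rule, but its efficacy population asks for one cycle of treatment without specifying combination. The SAP is therefore the narrower of the two.

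**3. Who can have samples but no scan**

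Protocol 10.3.1 requires imaging at least every 12 weeks, 12 × 7 = 84 days. The Run-In is 21 days and a combination cycle is 28. Assume no gap between the two phases.

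- Counted from Run-In Day 1: study day 84 is combination day 84 − 21 = 63, and 63 − 2 × 28 = 7, so cycle 3, day 7.
- Counted from combination Day 1: study day 21 + 84 = 105, which is combination day 84 = 3 × 28, the end of cycle 3.
- Cycles 1 and 2 end on study day 21 + 56 = 77, before either date.

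Planned plasma samples (Protocol 10.4.6) are 4 on Day 1, 3 on Day 8 and 1 on Day 15 of the Run-In, so 8, then 1 on Day 7 of each combination cycle. A patient who stops during cycle 2 after Day 7 can have 8 + 2 = 10 plasma samples and no required scan. The serial PK sampling is entirely in the Run-In, so the scan rule can discard a complete profile. Investigators may scan earlier, so these dates are upper limits.

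Replacement patients (Protocol 8.5) enter at Phase Ib cycle 1 and have no Run-In sampling, so they do not restore a lost profile.

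**4. Size**

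One such patient is 1/16 = 6.25% of the planned Phase I patients. If 1 to 4 patients are affected (my assumption), 15 to 12 remain.

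For an illustrative correlation r = 0.5 (also an assumption), the 95% interval is tanh(atanh(r) ± 1.96/√(n − 3)):

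- n = 16: 0.01 to 0.80
- n = 15: −0.02 to 0.81
- n = 12: −0.10 to 0.83
- n = 8: −0.32 to 0.89

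Precision is poor at every size, and losing one patient changes it little. The case rests on the missing analysis and the conflicting population, not on lost precision.

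**5. Analytes**

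Ceramide and ENOX2 appear in both protocol lists. Sphingosine-1-phosphate (a lipid) appears in one and sphingosine kinase (an enzyme) in the other. The SAP names no analyte, so it does not settle the matter.

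**The case against.** The strongest reply is that biomarker data are not lost. SAP 8.6 treats biomarkers as a safety analysis, and section 11 uses the Safety population for the biomarker table and figure. This stands. A reader might infer from 3.1 that Run-In biomarker samples from patients who stop early would be left out of the biomarker outputs; section 11 says otherwise. What remains is the conflict between 3.1 and 11, the silence of 7.3 on population, and the restriction on the PK outputs.

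Second, the objective in SAP 2.3 and Protocol 6.2 concerns treatment with carboplatin, so a patient who stops in the Run-In cannot inform it. This also stands for the biomarker objective as worded there. Those patients do matter for the PK objective, which is not limited to the combination.

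Third, a reader might infer that the selection must weaken any relation between biomarkers and toxicity. Nothing in the documents establishes a direction; selection could distort the relation either way. Nor do they forecast many early stops: Protocol 10.1.1 does not expect the MTD to be reached, and Protocol 5.3 reports only mild monotherapy fatigue in earlier studies.

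Fourth, the plan is descriptive, adverse events are tabulated with subject identification, all data are listed, and biomarker reporting depends on an assay being developed (SAP 8.6). A patient-level comparison could therefore be assembled afterwards. That is true, but it would not be pre-specified. A planned plot or table is itself descriptive, so the absence of hypothesis tests does not excuse the gap. The assay condition does not cover plasma idronoxil.

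Finally, the analyte conflict is a protocol matter and not a fault of SAP 7.3. Agreed; it is kept separate here.

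**Conclusion.** The point holds in three parts.

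- The toxicity half of a stated secondary objective has no analysis in the SAP, for biomarkers or for plasma idronoxil. This rests on the text alone.
- The PK/biomarker population carries a scan requirement that is irrelevant to PK. It removes patients with usable plasma but no scan from the plasma concentration and PK coefficient outputs, and it contradicts section 11 on biomarkers. This reads the subset sentence as inside both populations, its ordinary meaning; if the union was intended, the SAP should say so.
- The protocol's two analyte lists disagree.

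The number of patients affected cannot be derived from the documents. It depends partly on whether patients with severe Run-In toxicity leave the study, on which Protocol 9.4 and the text after Table 3 differ; those passages must be reconciled. The primary objectives are not touched. This should be corrected before the SAP is finalised, as a modest repair to a secondary objective whose biomarker part depends on assay development.

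**What to change.** - **SAP 7.3:** add a descriptive plot and table of biomarker levels and plasma idronoxil levels against worst CTCAE grade and DLT status. State the sample used (Day 7, 1 hour after dosing, is the only scheduled combination sample) and the period over which the worst grade is taken. Show levels as well as change from baseline, because replacement patients have no scheduled pre-dose sample. Keep the existing condition on assay availability for biomarkers.
- **SAP 3.1:** define the PK/biomarker population as all safety-population patients with usable plasma or biomarker data, retaining the exclusion for deviations that affect the data. Use the efficacy subset only when relating levels to response. Make the matching change in Protocol 13.2, or record the departure under SAP section 10.
- **SAP 11:** list the new outputs and use the same population names as 3.1.
- **Protocol synopsis and 10.2.3, separately:** give one analyte list and repeat it in the SAP.

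The cost is wording and a small amount of programming. No samples, visits, patients or tests are added.

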8. SAFETY ANALYSES

8.1 Exposure to study treatments

Exposure to study treatments will be calculated as date of last treatment minus date of start of treatment + 1. If unknown, the date of last treatment will be estimated using the last visit date minus 1 and imputed.

8.2 Adverse events

Adverse events will be coded by MedDRA SOC and Preferred Term, summarised and tabulated for the safety population in the monotherapy arm (phase 1a), in combination arm (phase 1b) with low dose (AUC4) carboplatin and with high dose (AUC6) carboplatin and overall treatment. For each preferred term the number and percent of subjects reporting each adverse event will be tabulated by cohort and 'Overall'. These include:

- Adverse event summary table
- Adverse events occurring prior to study commencement
- All adverse events occurring after study commencement
- Most common (>15 %) treatment-emergent adverse events in any cohort
- Treatment emergent adverse events that were possibly, likely or certainly related to the study medication
- Serious adverse events
- Severe adverse events
- Adverse events causing withdrawal
- All adverse events by maximum severity and relationship to study treatment, with subject identification.

8.3 Serious adverse events

Serious adverse events will be tabulated in the same way as all adverse events. In addition, anecdotal descriptions of each serious adverse event will be provided.

8.4 Vital signs

Vital sign variables, including standing and supine systolic and diastolic blood pressure, pulse, respiratory rate, and body temperature with change from Baseline will be summarised and tabulated by cohort and study visit (cycle and cycle day) by cohort.

8.5 Laboratory safety measurements

Serum biochemistry values, with change from Baseline and the number of clinically significant results will be summarised by cycle, cycle day and cohort. If multiple units are detected for any parameters, conversion of appropriate records to a common unit will be completed prior to summary and tabulation.

Haematology values, with change from Baseline and the number of clinically significant results will be summarised by cycle, cycle day and cohort. If multiple units are detected for any parameters, conversion of appropriate records to a common unit will be completed prior to summary and tabulation.

Urinalysis results for categorical measures will be summarised and tabulated, with change from Baseline (worsened, no change or improved) by cycle, cycle day and cohort. Continuous measures, pH and specific gravity, will be summarised and tabulated separately in a similar manner.

Urine microscopy results will be summarised and tabulated by cycle, cycle day and cohort.

8.6 Other safety analyses

Physical examination results will be summarised and tabulated by body system, cycle and cycle day and cohort, with change from Baseline (Abnormal to normal, Normal to abnormal).

ECG parameters will be summarised and tabulated by cycle, cycle day and cohort. ECG findings will summarised and tabulated separately by cycle, cycle day and cohort.

Biomarker values will be summarised and tabulated, with change from Baseline by cycle, cycle day and cohort for available data, dependent on the development of the specific biomarker assay.

9. INTERIM ANALYSES

Not applicable.

Data will be reviewed periodically to determine that DLTs are not occurring and to approve recruitment into later phases of the study.

10. CHANGES FROM THE PROTOCOL

All changes in procedures from the protocol will be documented in the final clinical study report.

11. TABLE AND FIGURE LISTINGS

Table Section	Table Title (Population)
Section 10.1	Patient disposition (All populations)
	Completion and withdrawal (Safety population)
Section 11.2	Demographics (Safety population)
	Disease history (Safety population)
	Prior medical history events (Safety population)
	Current medical history events (Safety population)
	Prior medications (Safety population)
	Concomitant medications (Safety population)
	New medications (Safety population)
	Prior chemotherapy (Safety population)
	ECOG status (Safety population)
Section 11.3	Compliance (Safety population)
Section 11.4	Tumour measurements (Efficacy population)
	RECIST response rates and durations (Efficacy population)
	Progression-free survival (Efficacy population)
	Overall survival (Efficacy population)
	Plasma concentrations (PK population)
	Pharmacokinetic coefficients (PK population)
Section 12.1	Exposure (Safety population)
Section 12.2	Summary of adverse events (Safety population)
	Pre-treatment adverse events (Safety population)
	Treatment emergent adverse events (Safety population)
	Treatment emergent adverse events considered possibly, probably or definitely related to study treatment (Safety population)
	Severe adverse events (Safety population)
	Adverse events resulting in withdrawal (Safety population)
Section 12.3	Deaths and serious adverse events
Section 12.4	Serum biochemistry (Safety population)
	Biochemistry shift table (Safety population)
	Haematology (Safety population)
	Haematology shift table (Safety population)
	Categorical urinalysis results (Safety population)

Section 12.5	Urinary pH and specific gravity (Safety population)
	Urinary microscopy (Safety population)
	Vital signs (Safety population)
	Physical examination (Safety population)
	ECG parameters (Safety population)
	ECG findings (Safety population)
	Biomarkers (Safety population)

Figure Section	Figure Title (Population)
Section 11.4	Tumour measurements (Efficacy population)
	Pattern of response by cohort (Efficacy population)
	Progression-free survival (Efficacy population)
	Overall survival (Efficacy population)
	Plasma concentrations by cohort (PK population)
Section 12.2	Most common preferred terms (Safety population)
Section 12.5	Biomarkers (for each parameter) (Safety population)
